9.3. Adverse Events

9.3.1. Solicited Events and Symptoms

Adverse event data is collected at each visit using specific questions and/or targeted physical examination. Based on the adverse reactions that have been observed with the use of auranofin in previous studies, the following solicited events are tracked: loose stools or diarrhea, abdominal pain, nausea with or without vomiting, constipation, anorexia, flatulence, dyspepsia, dysgeusia, pruritus, hair loss, urticaria, stomatitis, conjunctivitis, glossitis, hematuria, and rash. Hematologic, renal, or hepatic laboratory abnormalities are

picked up on testing at day 7. Adverse event collection continues until Day 28 (following three half-lives of the drug). As the drug is administered orally, no local event reactivity is recorded.

Table 35 and **Table 36** display the number, percentage, and 95% confidence interval for the percentage of subjects experiencing each solicited adverse event, by treatment group, separately for the amebiasis group and the giardiasis group. Solicited adverse events are also displayed graphically. **Figure 5** displays the maximum severity of solicited symptoms per subject by day post treatment, for each treatment group and for both treatment groups combined, separately for each disease group and study population.

Solicited systemic events by subject will be presented in [Listing 19](#), [Listing 20](#), [Listing 21](#), and [Listing 22](#).

9.3.2. Unsolicited Adverse Events

Unsolicited adverse events will be coded to a Medical Dictionary for Regulatory Activities Terminology (MedDRA) version 18.1 or later. Adverse Events will be summarized using the number and percentage of subjects who experienced each event overall for the safety population. When calculating the incidence of adverse events (i.e., on a per subject basis), each subject will only be counted once for each PT and SOC and any repetitions of adverse events within a subject for a PT or SOC will be ignored; the denominator will be the total number of subjects in the safety population. All adverse events reported will be included in the summaries and analyses.

Table 37 through **Table 40** summarize the number and percentage of subjects experiencing unsolicited adverse events by MedDRA System Organ Class and Preferred Term, severity, and relationship, by treatment, disease group, and study population.

A listing of serious adverse events, sorted by study population, disease group, and treatment group, is presented in **Table 41**. Listings of non-serious, unsolicited, moderate or severe adverse events, separately for each disease group and study population, are presented in **Table 42** and **Table 43**.

Unsolicited adverse events are also displayed graphically. **Figure 6** and **Figure 7** display the frequency of unsolicited adverse events by MedDRA System Organ Class by treatment group, separately for each disease group and study population. **Figure 8** and **Figure 9** display the incidence of adverse events by MedDRA System Organ Class by treatment group, separately for each disease group and study population. **Figure 10** and **Figure 11** summarize the frequency of unsolicited adverse events by severity for each treatment group and overall, separately for each disease group and study population. **Figure 12** and **Figure 13** display the incidence of unsolicited adverse events by severity for each treatment group and overall, separately for each disease group and study population. **Figure 14** and **Figure 15** display the frequency of unsolicited adverse events by MedDRA System Organ Class and relationship to treatment, by treatment group, separately for each disease group and study population. **Figure 16** and **Figure 17** display the incidence of unsolicited adverse events by MedDRA System Organ Class and relationship to treatment, by treatment group, separately for each disease group and study population. **Figure 18** and **Figure 19** display the frequency of unsolicited adverse events by relationship to treatment, by treatment group, separately for each disease group and study population. **Figure 20** and **Figure 21** display the incidence of unsolicited adverse events by relationship to treatment, by treatment group, separately for each disease group and study population.

Unsolicited adverse events by subject will be presented in [Listing 23](#) and [Listing 24](#), separately for each disease group and study population.

9.4. Deaths, Serious Adverse Events and other Significant Adverse Events

Section 14.3.3 will include narratives of deaths, and other serious and significant adverse events.

9.5. Pregnancies

Auranofin is a Category C drug whose use is not recommended in pregnant women because of studies in pregnant rabbits and rats with decreased maternal and fetal weight and litter size with 4-50X the human daily dose. This trial excludes pregnant women based on a pregnancy test during screening and requires two forms of contraception for the length of the trial (5-7 days) and for three half-lives of the drug (total 4 months). For any subjects in the Safety population who became pregnant during the study, study medication was stopped. Every attempt will be made to follow these subjects to completion of pregnancy to document the outcome, including information regarding any complications with pregnancy and/or delivery. A listing of pregnancies and outcomes will be presented ([Listing 37](#) through [Listing 41](#)).

9.6. Clinical Laboratory Evaluations

Laboratory parameters include white blood cell count, hemoglobin, hematocrit, platelets, BUN, Creatinine, AST, ALT, and urine protein, all measured during screening and on Study Day 7. Units and severity grading for the labs are summarized in [Table 7](#).

The distribution of laboratory results by maximum severity, study day and treatment group will be presented, separately for each disease group and study population, in [Table 46](#) through [Table 50](#). Abnormal laboratory results related to study treatment will be summarized by maximum severity, study day, and treatment group in [Table 51](#) through [Table 58](#), separately by disease group and study population. Descriptive statistics including mean, standard deviation, median, minimum and maximum values by study day, for each laboratory parameter, will be summarized separately for each disease group and study population in [Table 59](#) through [Table 66](#). Note that in general, summaries include only scheduled labs: unscheduled follow-up labs will be excluded from summaries but included in the listings. These include summaries at each time point as well as summaries in the change in observed values from baseline to Day 7. Listings of abnormal laboratory events (one listing for each disease group and study population) will be included in [Table 44](#) and [Table 45](#). Time trends of laboratory values will be graphically displayed in [Figure 22](#) and [Figure 23](#). Listings for all laboratory values will be provided, separately for each disease group and study population, in [Listing 25](#) through [Listing 30](#).

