9.2.4 Serious Adverse Events

An adverse event or suspected adverse reaction is considered “serious” if, in the view of either the investigator or sponsor, it results in any of the following outcomes:

- Death,
- a life-threatening adverse event*,
- inpatient hospitalization or prolongation of existing hospitalization,
- a persistent or significant incapacity or substantial disruption of the ability to conduct normal life functions, or
- a congenital anomaly/birth defect.
- Important medical events that may not result in death, be life-threatening, or require hospitalizations may be considered serious when, based upon appropriate medical judgment they may jeopardize the patient or subject and may require medical or surgical intervention to prevent one of the outcomes listed in this definition. Examples of such medical events include allergic bronchospasm requiring intensive treatment in an emergency room or at home, blood dyscrasias or convulsions that do not result in inpatient hospitalization, or the development of drug dependency or drug abuse.

* Life-threatening adverse event. An adverse event is considered “life-threatening” if, in the view of either the investigator or sponsor, its occurrence places the patient or subject at immediate risk of death. It does not include an adverse event, had it occurred in a more severe form, might have caused death.

All SAEs will be:

- recorded on the appropriate AE eCRF
- followed through resolution by a study clinician
- reviewed and evaluated by a study clinician

9.2.5 Procedures to be Followed in the Event of Abnormal Laboratory Test Values or Abnormal Clinical Findings

The site principal investigator or appropriate co-investigator is responsible for reporting all AE/SAEs that are observed or reported during the study, regardless of the relationship to study product. AE/SAEs, abnormal clinical laboratory test values, or abnormal clinical findings will

be documented, reported, and followed until levels return to baseline or until the abnormal value is determined to be not clinically significant.

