14.3.5 Displays of Laboratory Results

Table 46: Laboratory Results by Parameter, Maximum Severity, Study Day, and Treatment Group, Asymptomatic Amebiasis Group - Any Laboratory Parameter

Any laboratory parameter	Treatment Group	N	None		Mild/Grade 1 (Low)		Mild/Grade 1 (High)		Moderate/Grade 2 (Low)		Moderate/Grade 2 (High)		Severe/Grade 3 (Low)		Severe/Grade 3 (High)		Missing	
			n	%	n	%	n	%	n	%	n	%	n	%	n	%	n	%
Baseline	Auranofin, 6 mg	x	x	x.x	x	x.x	x	x.x	x	x.x	x	x.x	x	x.x	x	x.x	x	x.x
	Placebo																	
Day 7	Auranofin, 6 mg																	
	Placebo																	

Repeat for symptomatic study population.

Table 47: Laboratory Results by Parameter, Maximum Severity, Study Day, and Treatment Group, Asymptomatic Amebiasis Group - White Blood Cell Count

White Blood Cell Count	Treatment Group	N	None		Mild/Grade 1 (Low)		Mild/Grade 1 (High)		Moderate/Grade 2 (Low)		Moderate/Grade 2 (High)		Severe/Grade 3 (Low)		Severe/Grade 3 (High)		Missing	
			n	%	n	%	n	%	n	%	n	%	n	%	n	%	n	%
Baseline	Auranofin, 6 mg	x	x	x.x	x	x.x	x	x.x	x	x.x	x	x.x	x	x.x	x	x.x	x	x.x
	Placebo																	
Day 7	Auranofin, 6 mg																	
	Placebo																	

Repeat for symptomatic study population.

Table 48: Laboratory Results by Parameter, Maximum Severity, Study Day, and Treatment Group, Asymptomatic Amebiasis Group - Hemoglobin

Hemoglobin	Treatment Group	N	None		Mild/ Grade 1		Moderate/ Grade 2		Severe/ Grade 3		Missing	
			n	%	n	%	n	%	n	%	n	%
Baseline	Auranofin, 6 mg	x	x	x.x	x	x.x	x	x.x	x	x.x	x	x.x
	Placebo											
Day 7	Auranofin, 6 mg											
	Placebo											

*Repeat for symptomatic study population.***Table 49: Laboratory Results by Parameter, Maximum Severity, Study Day, and Treatment Group, Asymptomatic Amebiasis Group - Hematocrit**

Hematocrit	Treatment Group	N	None		Mild/ Grade 1		Moderate/ Grade 2		Severe/ Grade 3		Missing	
			n	%	n	%	n	%	n	%	n	%
Baseline	Auranofin, 6 mg	x	x	x.x	x	x.x	x	x.x	x	x.x	x	x.x
	Placebo											
Day 7	Auranofin, 6 mg											
	Placebo											

Repeat for symptomatic study population.

Table 50: Laboratory Results by Parameter, Maximum Severity, Study Day, and Treatment Group, Asymptomatic Amebiasis Group - Platelets

Platelets	Treatment Group	N	None		Mild/ Grade 1 (Low)		Mild/ Grade 1 (High)		Moderate/ Grade 2 (Low)		Moderate/ Grade 2 (High)		Severe/ Grade 3 (Low)		Severe/ Grade 3 (High)		Missing	
			n	%	n	%	n	%	n	%	n	%	n	%	n	%	n	%
Baseline	Auranofin, 6 mg	x	x	x.x	x	x.x	x	x.x	x	x.x	x	x.x	x	x.x	x	x.x	x	x.x

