14.3.6 Displays of Vital Signs

Table 67: Vital Signs by Assessment, Maximum Severity, Study Day, and Treatment Group, Amebiasis Group - Any Assessment

This table series will be repeated for the symptomatic study population.

Time Point	Treatment Group	N	None		Mild		Moderate		Severe		Missing	
			n	%	n	%	n	%	n	%	n	%
Baseline	Auranofin, 6 mg	x	x	x.x	x	x.x	x	x.x	x	x.x	x	x.x
	Placebo											
Day 1	Auranofin, 6 mg											
	Placebo											
Day 2	Auranofin, 6 mg											
	Placebo											
Day 3	Auranofin, 6 mg											
	Placebo											
Day 4	Auranofin, 6 mg											
	Placebo											
Day 5	Auranofin, 6 mg											
	Placebo											
Day 6	Auranofin, 6 mg											
	Placebo											
Day 7	Auranofin, 6 mg											
	Placebo											
Day 14	Auranofin, 6 mg											
	Placebo											
Day 28	Auranofin, 6 mg											
	Placebo											
Max Severity Post Baseline	Auranofin, 6 mg											
	Placebo											

Note: The “Max Post Baseline” rows indicate the maximum severity experienced by each subject at any time point post baseline, including unscheduled assessments. N=Number of subjects in the Safety population with non-missing values.

Table 68: Vital Signs by Assessment, Maximum Severity, Study Day, and Treatment Group, Amebiasis Group - Fever

Time Point	Treatment Group	N	None		Mild		Moderate		Severe		Missing	
			n	%	n	%	n	%	n	%	n	%
Baseline	Auranofin, 6 mg	x	x	x.x	x	x.x	x	x.x	x	x.x	x	x.x
	Placebo											
Day 1	Auranofin, 6 mg											
	Placebo											
Day 2	Auranofin, 6 mg											
	Placebo											
Day 3	Auranofin, 6 mg											
	Placebo											
Day 4	Auranofin, 6 mg											
	Placebo											
Day 5	Auranofin, 6 mg											
	Placebo											
Day 6	Auranofin, 6 mg											
	Placebo											
Day 7	Auranofin, 6 mg											
	Placebo											
Day 14	Auranofin, 6 mg											
	Placebo											
Day 28	Auranofin, 6 mg											
	Placebo											
Max Severity Post Baseline	Auranofin, 6 mg											
	Placebo											

"Max Post Baseline" rows indicate the maximum severity experienced by each subject at any time point post including unscheduled assessments. N=Number of subjects in the Safety population with non-missing values.

Table 69: Vital Signs by Assessment, Maximum Severity, Study Day, and Treatment Group, Amebiasis Group - Systolic Blood Pressure (Hypertension/Hypotension)

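### The laboratory severity tables have no post-baseline maximum, so a peak grade found on follow-up after Day 7 appears in no by-arm laboratory table

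*SAP*

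**What the plan says.** SAP 9.6 lists the laboratory parameters (white cells, hemoglobin, hematocrit, platelets, BUN, creatinine, AST, ALT, urine protein) as "all measured during screening and on Study Day 7". It then promises by-arm severity tables: "The distribution of laboratory results by maximum severity, study day and treatment group will be presented". The rule on repeat tests follows in the same section: in general, only scheduled tests are summarized, and "unscheduled follow-up labs will be excluded from summaries but included in the listings". No exception to that general rule is defined.

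Protocol 9.2.5 says that abnormal laboratory values will "be documented, reported, and followed until levels return to baseline or until the abnormal value is determined to be not clinically significant". Protocol 6.3 adds that Day 7 abnormalities are evaluated as adverse events and followed.

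The vital-sign shells (SAP Appendix 1, Tables 67-78) carry an extra row, *Max Severity Post Baseline*. Its note says that it shows "the maximum severity experienced by each subject at any time point post baseline, including unscheduled assessments".

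**The concern.** There is one scheduled laboratory draw after dosing starts. Later values will exist mainly for subjects whose Day 7 result was abnormal, and those are the values that the summary rule sets aside. A table titled by maximum severity that cannot show a later, worse value may be read as giving the worst grade reached when it does not.

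The stake is the by-arm picture of laboratory toxicity. Protocol 2.3.1 and 9.1 list hematologic, hepatic and renal reactions to auranofin, and Protocol 9.4.1 has the DSMB notified of any Grade 3 drug-related event. Whether an arm's worst laboratory grade was 1 or 3 is therefore something a reader of the study report will want to see by arm. The same SAP already provides a post-baseline maximum for vital signs and gives no reason for omitting one for laboratory results.

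**Working it through.** The plan gives no figure to reproduce. The check sets the provisions side by side and traces a result through them.

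1. **Scheduled draws after baseline: one.** SAP 9.6, Protocol 8.2.1 and Protocol Appendix A all give screening (Visit 00B) and Day 7 only.
2. **Follow-up draws are unscheduled.** Protocol 9.2.5 and 6.3 call for follow-up of abnormal values but set no repeat-test visit.
3. **Unscheduled draws are, in general, left out of summaries** (SAP 9.6).
4. **Shells.** Tables 46-58 have Baseline and Day 7 rows only. With one post-baseline value per parameter, the maximum in each single-parameter table is simply the Day 7 grade. Figures 22 and 23 also stop at Day 7.
5. **Vital signs.** Tables 67-78 have the same kind of by-visit rows plus the post-baseline maximum row, and unscheduled assessments are stated to enter that row.

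**Hypothetical trace, grades from Protocol 9.2.3.** An amebiasis subject has platelets of 110 on Day 7 (Grade 1, 100-130) and 45 on a repeat test (Grade 3, below 50):

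| Display | What it shows |
|---|---|
| Table 50, and Table 54 if related | Day 7: Grade 1 |
| Table 62 and Figure 22 | Day 7 value of 110 |
| Table 44 and Listing 25 | Both values, by subject, with treatment group |
| Tables 37-38 (unsolicited adverse events) | Grade 3 only if laboratory adverse events are counted there; the SAP does not say |

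For chemistry the by-arm display is thinner. An ALT of 180 on Day 7 (Grade 1, 70.1-200) that rises to 320 (Grade 3, above 300) has no table of its own, because the single-parameter shells cover only white cells, hemoglobin, hematocrit and platelets. It could appear by arm only in Table 46, which pools all parameters, and there as Grade 1. SAP 9.6 promises Tables 46-50 for each disease group, but those shells are titled for amebiasis and are marked for repetition only in the symptomatic population.

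**Scale.** One subject in a planned arm is 1/34 = 2.9%. The asymptomatic cohort has 34 subjects in total (SAP 6.2). If they were spread evenly over four disease-by-arm cells, which is an assumption, a cell would hold 34/4 = 8.5 and one subject would be 1/8.5 = 11.8%. These figures show what one subject weighs. The documents give no rate of repeat testing or of worsening, so they do not say how many subjects would be affected.

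**The case against.** The strongest reply is that worsening already has a by-arm route through adverse events. The limits in Protocol 9.2.3 that trigger an adverse event report coincide with the Grade 1 boundaries, apart from a platelet count of exactly 130, so essentially every graded abnormality should be reported. Protocol 9.2.1 has changes in severity documented. SAP 9.3.2 says that all reported adverse events enter the summaries, and the notes to Tables 37-40 count each subject at the highest severity. Drug-related Grade 3 events also go to the DSMB individually.

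This reduces the harm but does not clearly close the gap. Tables 37-40 cover unsolicited events, and the SAP never says that laboratory events are among them. SAP 9.3.1 mentions laboratory abnormalities under solicited events, yet Tables 35-36 have no laboratory rows. Elsewhere the SAP treats laboratory results as a separate stream, with their own grading scale (Table 7), listing (Tables 44-45) and treatment-related tables (51-58).

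Three further replies stand. The Day 7 row is a by-visit row and is right for Day 7. In Table 46, maximum can fairly mean the worst grade across parameters on one day. The worsened values also remain visible with treatment group in Tables 44-45 and in the subject listings. These limit the point to a missing summary row.

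It can also be said that the vital-sign row condenses many visits, whereas laboratory results have one scheduled post-baseline draw. That explains the layout. It does not supply the peak grade once follow-up tests exist.

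**Conclusion.** The point holds as a reporting gap that should be closed. Followed as written, the plan shows the peak grade of an abnormality that worsens after Day 7 in no by-arm laboratory table. This assumes that the general rule in SAP 9.6 is applied without unstated exceptions and that some abnormal Day 7 results are retested. No endpoint, test or analysis population changes.

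Several stronger readings are tempting, and the documents do not support them:

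- **Subjects are misgraded or data are lost.** The Day 7 grade is correct, and later values stay in the listings.
- **Every repeat value is dropped from every summary, and all abnormalities are retested until they resolve.** The SAP rule holds only in general, and follow-up may stop when a value is judged not clinically significant.
- **Peak values probably fall after Day 7.** Nothing in the documents shows this. The Phase I study in 15 healthy volunteers (Protocol 2.3.1) reported no clinically meaningful laboratory changes.
- **Day 7 is a dosing-day value that cannot show later effects.** Giardiasis dosing ends on Day 5, so in that group the Day 7 draw comes after treatment.
- **The vital-sign tables follow the opposite rule throughout.** Unscheduled vital signs are stated to enter only the maximum row.

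**What to change.** - Keep the Baseline and Day 7 rows of Tables 46-58 on scheduled values.
- Add a *Max Severity Post Baseline* row that includes unscheduled results to each of these tables, with the footnote already used in Tables 67-78.
- Apply the row to the any-parameter table for each disease group, adding a giardiasis shell, so that hepatic, renal and urine-protein peaks are captured.
- In SAP 9.6, limit the scheduled-only rule to the by-visit rows and to summary-statistics Tables 59-66.

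The cost is one row and footnote per shell, one added shell, a sentence in SAP 9.6 and a little programming; no new data are needed. One limit comes with the row: it will mostly reflect subjects retested because of an abnormal value, and the footnote should say so. It will not reveal a late abnormality in a subject who was normal on Day 7 and was not tested again.

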9.7. Vital Signs and Physical Evaluations

Vital signs include height and weight, temperature, systolic and diastolic blood pressure, and pulse. These were assessed during screening and on every scheduled visit. Targeted physical exams were conducted on the same days and looked for abdominal pain, hair loss, urticaria, rashes, stomatitis, conjunctivitis, and glossitis. Refer to [Table 6](#) for vital sign grading criteria.

Vital signs will be tabulated by visit, severity, and treatment group, separately for each disease group and study population ([Table 67](#) through [Table 78](#)). Vital sign listings will be provided for subjects in the Safety population ([Listing 31](#) and [Listing 32](#)). Physical exam findings will be listed in [Listing 33](#) and [Listing 34](#).

9.8. Concomitant Medications

Concomitant medications will be coded to the Anatomical Therapeutic Classification using the WHO Drug Dictionary. The use of prior and concomitant medications taken during the study will be recorded on the CRFs. A by-subject listing of concomitant medication use will be presented ([Listing 35](#) and [Listing 36](#)). The use of concomitant medications during the study will be summarized by WHO drug classification and treatment group, separately for each disease group and study population, for the Safety population ([Table 79](#) and [Table 80](#)).

10. PHARMACOKINETICS

Not applicable.

11. IMMUNOGENICITY

Not applicable.

12. OTHER ANALYSES

Not applicable.

13. REPORTING CONVENTIONS

P-values ≥ 0.001 will be reported to 3 decimal places; p-values less than 0.001 will be reported as “ <0.001 ”. The mean, standard deviation, and any other statistics other than quantiles, will be reported to one decimal place greater than the original data. Quantiles, such as median, or minimum and maximum will use the same number of decimal places as the original data. Proportions will be presented as two decimal places; values <0.01 will be presented as “ <0.01 ”. Percentages will be reported to the nearest whole number; values $<1\%$ will be presented as “ <1 ”. Estimated parameters, not on the same scale as raw observations (e.g. regression coefficients) will be reported to 3 significant figures.

